1.1.2. Study Drug Development

1.1.2.1. Nonclinical Studies

A comprehensive nonclinical program including dermal tolerance, dermal sensitization, and general toxicology studies have been conducted in multiple species (rat, guinea pig, rabbit, minipig, and monkey) for abaloparatide-SC and is considered supportive for abaloparatide-sMTS. Additional dermal tolerance, dermal sensitization, and general toxicology studies with abaloparatide-sMTS are ongoing or planned. The findings from the completed studies support the conclusion that abaloparatide-sMTS is well tolerated, with no new significant safety risks identified. Full details of the nonclinical development program for abaloparatide are provided in the Investigator's Brochure.

1.1.2.2. Clinical Studies

There are 19 completed and ongoing clinical studies which comprise the abaloparatide (SC and transdermal [sMTS]) clinical development programs. The abaloparatide-SC clinical trial program consists of 11 clinical trials, including a large pivotal Phase 3 study (BA058-05-003) followed by an open-label extension (BA058-05-005).

The abaloparatide-sMTS clinical trial program includes a Phase 1 study with abaloparatide-sMTS administration (BA058-05-015) to select an optimized formulation and dose for abaloparatide-sMTS to be used in the Phase 3 study.

Additional details for these clinical studies can be found in the most recent Investigator's Brochure.

1.1.2.2.1. Abaloparatide-SC

In the pivotal Phase 3 study (Study BA058-05-003, the ACTIVE trial), 2,463 postmenopausal osteoporotic women were randomized to receive daily 80 µg abaloparatide-SC (n=824), placebo (n=821), or teriparatide 20 µg (n=818) (rhPTH 1-34) for 18 months. In this trial, abaloparatide-SC and teriparatide significantly reduced the risk of new morphometric vertebral fractures by 86% and 80%, respectively, compared to placebo. Abaloparatide-SC significantly reduced nonvertebral, major osteoporotic, and clinical fractures compared to placebo. Compared to teriparatide, abaloparatide significantly reduced major osteoporotic fractures. The Kaplan-Meier plots indicate an early and sustained fracture risk reduction of nonvertebral, major osteoporotic, and clinical fractures with abaloparatide-SC treatment. Abaloparatide-SC was generally safe and well tolerated in postmenopausal women with osteoporosis; the most common adverse reactions (incidence ≥5%) were hypercalciuria, dizziness, nausea, headache, and palpitations. Consistent with reduced abaloparatide-SC-mediated calcium mobilization, the rates of hypercalcemia were lower in the abaloparatide-SC group compared to the teriparatide group.

In the ACTIVExtend trial (Study BA058-05-005), subjects who were in the abaloparatide-SC or placebo arms were transitioned to oral alendronate 70 mg weekly. Subjects who received 18 months of abaloparatide-SC followed by 6 months of alendronate experienced no new morphometric vertebral fractures from Study BA058-05-005 baseline and continued to have statistically significant reductions in nonvertebral, major osteoporotic, and clinical fractures when compared to subjects who previously received 18 months of placebo followed by 6 months of alendronate. These results validate the osteoporosis treatment paradigm of build (with an anabolic agent) and then maintain and consolidate gains (with an anti-resorptive agent).

Abaloparatide-SC demonstrated an increase in BMD at the lumbar spine, total hip, femoral neck, and ultradistal radius in osteoporosis subjects, consistent with the fracture risk reduction. The results from the ACTIVE trial and the first 6 months of the ACTIVExtend trial, together with the entire data set from the abaloparatide-SC development program, support the safety and efficacy of abaloparatide-SC for the reduction of fractures in postmenopausal women with osteoporosis.

In Study BA058-05-005, after 25 and 43 months of treatment (18 months abaloparatide, 1 month transition, followed by 6 or 24 months of alendronate respectively), the reductions in new vertebral fracture for abaloparatide/alendronate vs placebo/alendronate-treated subjects show long-term vertebral fracture reduction of 90% after 25 months and 84% after 43 months. In the ACTIVExtend trial the adverse events (AEs) were comparable between subjects previously treated with abaloparatide-SC and the previous placebo group. The incidences of cardiovascular AEs, including serious adverse events (SAEs), were similar between groups.

There have been no cases of osteosarcoma, osteonecrosis of the jaw, or atypical femoral fracture in the entire abaloparatide-SC clinical development program. In nonclinical studies, a dose-dependent incidence of osteosarcomas was seen in both male and female rats treated with abaloparatide and in a positive control group treated with hPTH(1-34).

Overall, the clinical results of abaloparatide-SC-mediated early vertebral and nonvertebral fracture risk reduction and increases in BMD are consistent with the known anabolic mechanism of action, changes in bone turnover markers, and nonclinical results.

1.1.2.2.2. Abaloparatide-sMTS

To date, several different abaloparatide-sMTS formulations have been evaluated in a total of 4 Phase 1 studies and one Phase 2 study, including an abaloparatide-sMTS phosphate buffered saline (PBS) formulation (abaloparatide-sMTS PBS) and an optimized formulation (abaloparatide ZnCl₂·HCl).

The abaloparatide-sMTS PBS formulation has similar abaloparatide maximum concentration, but lower abaloparatide area under the concentration-time curve (AUC) than the reference abaloparatide-SC 80 µg treatment. This abaloparatide-sMTS formulation was evaluated in 3 completed Phase 1 studies in healthy postmenopausal women, Studies BA058-05-004, BA058-05-006, and BA058-05-008. These studies were conducted to evaluate the pharmacokinetics (PK), safety, and local tolerability of different doses of abaloparatide-sMTS and to evaluate the impact of the application site and the duration of application (wear time) on PK, safety, and local tolerability.

A Phase 2, dose-range-finding study, Study BA058-05-007, was also conducted with the abaloparatide-sMTS PBS formulation to evaluate the PK, efficacy, and safety of 3 doses of abaloparatide-sMTS (50, 100, and 150 μ g) compared to 80 μ g abaloparatide-SC and placebo-sMTS in postmenopausal women with osteoporosis. The results from this study with the abaloparatide-sMTS PBS formulation did not support the selection of this abaloparatide-sMTS formulation for further clinical development, although it did provide important insights into the exposure-response relationship between abaloparatide-sMTS and increases in BMD.

BA058-05-015 was a Phase 1 study to select an optimized formulation and dose for abaloparatide-sMTS to be used in the Phase 3 study. From the PK data in this clinical study, abaloparatide-sMTS Formulation W-1 (abaloparatide ZnCl₂·HCl) 300 µg applied to the thigh for 5 minutes was selected for further clinical development.

Full details of the results of clinical trials conducted with abaloparatide-SC and abaloparatide-sMTS are provided in the Investigator's Brochure.

1.2. Study Rationale

The purpose of this study is to evaluate the comparability of abaloparatide-sMTS 300 μg based on lumbar spine BMD non-inferiority compared to abaloparatide-SC 80 μg at 12 months and to evaluate the safety and tolerability of abaloparatide-sMTS in the treatment of postmenopausal women with osteoporosis. The transdermal method of administration for abaloparatide may be preferred to an SC method by some subjects and may reduce a barrier for anabolic therapy.

1.3. Dose Rationale

The approved dose of abaloparatide-SC in the US for the treatment of postmenopausal women at high risk for fracture is 80 μg per day; this will be used as the comparator for the 300 μg abaloparatide-sMTS for the present study.

BA058-05-015 was a Phase 1 study initiated to select an optimized formulation and dose for abaloparatide-sMTS to be used in this study. From the PK data, it was determined that

abaloparatide-sMTS Formulation W-1 (abaloparatide $ZnCl_2 \cdot HCl)$ 300 µg applied to the thigh for 5 minutes provided a single-patch administration option with a similar PK profile (slow absorption with a similar time of maximum concentration and AUC) to abaloparatide-SC 80 µg and is expected to produce similar pharmacodynamic effects on BMD as the marketed abaloparatide-SC 80 µg treatment in the clinical setting. Additionally, abaloparatide-sMTS Formulation W-1 300 µg is expected to provide an acceptable safety profile for this Phase 3 non-inferiority BMD study.

2. STUDY OBJECTIVES AND ENDPOINTS

2.1. Objectives and Primary Endpoint

The objective of this study is to evaluate the non-inferiority of abaloparatide-sMTS 300 μg compared to abaloparatide-SC 80 μg based on lumbar spine BMD at 12 months and to evaluate the safety and tolerability of abaloparatide-sMTS in the treatment of postmenopausal women with osteoporosis.

The primary efficacy endpoint is the percent change from baseline in lumbar spine BMD at 12 months.

2.2. Secondary Endpoints

Secondary Efficacy Endpoints:

- Percent change from baseline in total hip BMD at 12 months
- Percent change from baseline in femoral neck BMD at 12 months

Additional Efficacy Endpoints:

- Percent change from baseline in lumbar spine BMD at 3 and 6 months
- Percent change from baseline in total hip BMD at 3 and 6 months
- Percent change from baseline in femoral neck BMD at 3 and 6 months

Other Endpoints

- Log ratio of post-baseline over baseline in serum procollagen type 1 N propeptide (s-PINP) at 1, 3, 6, and 12 months
- Log ratio of post-baseline over baseline in serum carboxy-terminal cross-linking telopeptide of type I collagen (s-CTX) at 1, 3, 6, and 12 months
- Plasma concentration of abaloparatide from sparse PK sampling

Safety and Tolerability Endpoints:

Treatment-emergent AEs (TEAEs), AEs of special interest (AESI), vital signs (orthostatic blood pressure, pulse rate, body temperature, and respiration rate), electrocardiograms (ECGs), laboratory tests (chemistry, hematology, coagulation, and urinalysis), local tolerance, and presence of anti-drug antibodies (ADAs)

3. STUDY DESIGN

3.1. Description of the Study Design

This is a randomized, open-label, non-inferiority, multicenter study of abaloparatide-sMTS compared with abaloparatide-SC for the treatment of women with postmenopausal osteoporosis. An overview of the design of the study is presented in Figure 1.

The study will consist of a Screening Period (up to 2 months), a Pretreatment Period (1 week), and a Treatment Period (12 months) with a final visit 1 month after the last dose of study drug (Follow-Up/End of Study [EOS] visit); 1 month is defined as 30 days in this study. Thus, subjects will participate in the study for up to 16 months.

[figure not shown]
Subjects will be randomized on Day 1 of the Treatment Period. During the Treatment Period, subjects will self-administer study drug once a day for 12 months and visit the study site on Days 1 and 14 and Months 1, 2, 3, 4, 5, 6, ,7 8, 9, 10, 11, and 12.

Eligible subjects will be randomized in a 1:1 ratio to either abaloparatide-sMTS or abaloparatide-SC using a permuted block randomization scheme. Both groups of subjects will undergo protocol-specified procedures, including BMD and bone turnover marker assessment.

All subjects will be provided calcium and vitamin D to ensure that their daily intake is 1,200 mg/day and 800 IU/day, respectively, or a dose determined by the Investigator and agreed by the Sponsor's Medical Monitor according to the subject's need.

All subjects will undergo safety, BMD, bone turnover markers, and fracture assessments at regular intervals according to the Schedule of Assessments and Procedures (Table 1).

Figure 1: Study Design

4. SELECTION OF STUDY POPULATION

In order to participate in this study, a subject must meet all of the following inclusion criteria and none of the exclusion criteria. Subjects who are screened and excluded from this study will be recorded in the electronic Case Report Form (eCRF) with the reason why they were screen failures.

4.1. Inclusion Criteria

Subjects will be included if they meet all of the following inclusion criteria:

- 1. Healthy ambulatory female from 50 to 85 years of age (inclusive) with postmenopausal osteoporosis
- 2. Postmenopausal for at least 5 years as demonstrated by a history of amenorrhea for at least 5 years
- 3. BMD T-score based on the female reference range as assessed by the central imaging vendor of:
 - a. Less than or equal to -2.5 and greater than -5.0 at the lumbar spine (L1–L4) or hip (femoral neck or total hip) by dual energy X-ray absorptiometry (DXA) and
 - i. Radiological evidence of 2 or more mild or 1 or more moderate lumbar or thoracic vertebral fractures, or

- ii. History of fragility fracture to the forearm, humerus, sacrum, pelvis, hip, femur, or tibia within the past 5 years
- b. Postmenopausal women older than 65 years who meet the fracture criteria (i or ii) but have a T-score of \leq -2.0 and > -5.0 may be enrolled
- c. Postmenopausal women older than 65 years who do NOT meet the fracture criteria may be enrolled if they have a BMD T-score \leq -3.0 and >-5 at the lumbar spine (L1-L4) or hip (femoral neck or total hip) by DXA
- 4. In good general health as determined by medical history and physical examination (including vital signs), has a body mass index of 18.5 to 33 kg/m², inclusive, and is without evidence of clinically significant abnormality in the opinion of the Investigator
- 5. Serum calcium (albumin-corrected), PTH (1-84), serum phosphorus, alkaline phosphatase, and thyroid stimulating hormone (TSH) values all within the normal range during the Screening Period. Any subject with an elevated alkaline phosphatase value and who meets all other entry criteria would be required to have a normal bone-specific alkaline phosphatase in order to be enrolled. Any subject with a TSH value outside of the normal range may be enrolled if their T3 and free T4 values are within the normal range
- 6. Serum 25-hydroxyvitamin D values must be $\geq 20 \text{ ng/mL}$
- 7. Resting 12-lead ECG at Screening shows no clinically significant abnormality
- 8. Systolic blood pressure is ≥ 100 and ≤ 155 mmHg, diastolic blood pressure is ≥ 40 and ≤ 95 mmHg, and pulse rate is ≥ 45 and ≤ 100 beats per minute (taken sitting or supine)
- 9. Has no clinically significant abnormality of serum hemoglobin, hematocrit, white blood cells, and platelets, or usual serum biochemistry, including electrolytes, renal function, liver function and serum proteins, that might be expected to interfere with the subject's health and/or medical treatment during the study.
- 10. Read, understood, and signed the written Informed Consent Form (ICF)

4.2. Exclusion Criteria

Subjects who meet any of the following exclusion criteria will be excluded from the study:

General exclusion criteria:

- 1. History of more than 4 spine fractures, mild or moderate, or any severe fractures based on Genant Semi-quantitative Scoring method on radiographic findings
- 2. Presence of abnormalities of the lumbar spine that would prohibit assessment of spinal BMD, defined as having at least 2 radiologically-evaluable vertebrae within L1–L4 as assessed by the central imaging review of the DXA images

Anatomically abnormal vertebrae are excluded if:

They are clearly abnormal and non-assessable within the resolution of the system;
 or

 There is a more than 1.0 T-score difference between the vertebra in question and adjacent vertebrae

- 3. Unevaluable hip BMD or subjects who have undergone bilateral hip replacement (unilateral hip replacement is acceptable)
- 4. History of bone disorders (eg, Paget's disease) other than postmenopausal osteoporosis
- 5. History of prior external beam or implant radiation therapy involving the skeleton, other than radioiodine
- 6. History of Cushing's disease, hyperthyroidism, hypo- or hyperparathyroidism, or malabsorptive syndromes within the past year
- 7. History of significantly impaired renal function (serum creatinine > 177 μ mol/L or > 2.0 mg/dL). If serum creatinine is > 1.5 and \leq 2.0 mg/dL, the calculated creatinine clearance (Cockcroft-Gault) must be \geq 37 mL/minute
- 8. History of any cancer within the past 5 years (other than basal cell or squamous cancer of the skin)
- 9. History of osteosarcoma at any time
- 10. Hereditary disorders predisposing to osteosarcoma
- 11. History of nephrolithiasis or urolithiasis within the past 5 years
- 12. Decrease of 20 mmHg or more in systolic blood pressure or 10 mmHg or more in diastolic blood pressure from supine to standing (5 minutes laying and 3 minutes standing) or any symptomatic hypotension at Screening
- 13. Application site is compromised by scars, inflammation, or skin conditions that may compromise uniformity of patch application or drug delivery (nevi, plaques, tattoos, scars, piercing, etc)
- 14. Any other medical condition, that, in the opinion of the Investigator, renders the subject unable or unlikely to complete the study, would interfere with the interpretation of study data, or produce significant risk to the subject

Medication-related exclusion criteria:

- 15. Known history of hypersensitivity to any of the test materials or related compounds
- 16. Prior treatment with PTH- or PTHrP-derived drugs or bone anabolic drugs including abaloparatide, teriparatide, or PTH (1-84)
- 17. Prior treatment with intravenous bisphosphonates at any time or oral bisphosphonates within the past 3 years. Subjects who have received a short course of oral bisphosphonate therapy (3 months or less) may be enrolled as long as the treatment occurred 6 or more months prior to enrollment
- 18. Prior treatment with selective estrogen receptor modulators (such as raloxifene or tamoxifen) in the past 6 months. Estrogens administered as hormone replacement therapy, with or without progestins, are not exclusionary

19. Treatment with fluoride or strontium in the past 5 years or prior treatment with gallium nitrate or bone-acting investigational agents at any time

- 20. Prior treatment with calcitonin or tibolone in the past 6 months
- 21. Treatment with denosumab within the past 18 months
- 22. Treatment with anticonvulsants that affect vitamin D metabolism (phenobarbital, phenytoin, carbamazepine, or primidone) or with chronic heparin within the 6 months prior to the Screening Period
- 23. Treated with anabolic steroids or calcineurin inhibitors (cyclosporin, tacrolimus) in the past 90 days
- 24. Daily treatment with corticosteroids within the 12 months prior to the Screening Period. Occasional use of low dose corticosteroids (for seasonal allergies or asthma) is not exclusionary. Use of low dose oral corticosteroids (eg, ≤ 5 mg/day of prednisone or the relative equivalent dose of another corticosteroid) is also not exclusionary
- 25. Participation in another clinical trial with any investigational drug or device within 90 days or 5 half-lives of the investigational drug (if known), whichever is longer, of study drug administration

Lifestyle-related exclusion criteria:

- 26. Abnormal nutritional status as assessed by the Investigator, vitamin D intake of ≥ 4,000 IU/day, or vitamin A intake of ≥ 10,000 IU/day. Short-term use of high doses of vitamin D to bolster endogenous vitamin D levels for study entry during the Screening Period is not exclusionary
- 27. Active drug or alcohol dependence or abuse (excluding tobacco or medicinal or recreational marijuana use where legal unless there is evidence of abuse) within 12 months of the Screening Period, or evidence of such abuse in the opinion of the Investigator

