- 5. Serum calcium (albumin-corrected), PTH (1-84), serum phosphorus, alkaline phosphatase, and thyroid stimulating hormone (TSH) values all within the normal range during the Screening Period. Any subject with an elevated alkaline phosphatase value and who meets all other entry criteria would be required to have a normal bone-specific alkaline phosphatase in order to be enrolled. Any subject with a TSH value outside of the normal range may be enrolled if their T3 and free T4 values are within the normal range
- 6. Serum 25-hydroxyvitamin D values must be ≥ 20 ng/mL
- 7. Resting 12-lead electrocardiogram at Screening shows no clinically significant abnormality.
- 8. Systolic blood pressure is ≥ 100 and ≤ 155 mmHg, diastolic blood pressure is ≥ 40 and ≤ 95 mmHg, and pulse rate is ≥ 45 and ≤ 100 beats per minute (taken sitting or supine)
- 9. No clinically significant abnormality of serum hemoglobin, hematocrit, white blood cells, and platelets, or usual serum biochemistry, including electrolytes, renal function, liver function and serum proteins, that might be expected to interfere with the subject's health and/or medical treatment during the study
- 10. Read, understood, and signed the written Informed Consent Form

Exclusion criteria:

Subjects who meet any of the following exclusion criteria will be excluded from the study:

General exclusion criteria:

- 1. History of more than 4 spine fractures, mild or moderate, or any severe fractures based on Genant Semi-quantitative Scoring method on radiographic findings
- 2. Presence of abnormalities of the lumbar spine that would prohibit assessment of spinal BMD, defined as having at least 2 radiologically-evaluable vertebrae within L1–L4 as assessed by the central imaging review of the DXA images.

Anatomically abnormal vertebrae are excluded if:

- They are clearly abnormal and non-assessable within the resolution of the system; or
- There is a more than 1.0 T-score difference between the vertebra in question and adjacent vertebrae
- 3. Unevaluable hip BMD or subjects who have undergone bilateral hip replacement (unilateral hip replacement is acceptable)
- 4. History of bone disorders (eg. Paget's disease) other than postmenopausal osteoporosis
- 5. History of prior external beam or implant radiation therapy involving the skeleton, other than radioiodine
- 6. History of Cushing's disease, hyperthyroidism, hypo- or hyperparathyroidism, or malabsorptive

- syndromes within the past year

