6.6. Imaging Procedures

All DXA measurements (BMD according to DXA) will be performed according to the procedures outlined in the Imaging Charter and Imaging Manuals which will be provided as separate documents. All DXA measurements will be assessed by a central imaging laboratory. Screening spine radiographs will be assessed locally.

6.6.1. **Dual Energy X-ray Absorptiometry**

All subjects will have areal BMD measurements taken via DXA of the lumbar spine, total hip, and femoral neck at Screening, Month 3, Month 6, and Month 12. Lumbar spine scans must include L1 through L4. Hip scans will include the entire proximal femur to about 2 cm below the lesser trochanter. For hip scans, the same side should be used for all scans at all visits measured. If a subject fractures the hip being examined during the study, no further scans of the hip will be acquired.

For screening purposes, DXA scans of the lumbar spine, total hip, and femoral neck taken up to 35 days prior to the beginning of the Screening Period may be used to enroll a subject in the study if the BMD T score criteria in Section 6.2.5 are met.

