## **2. SUBJECT ANALYSIS POPULATIONS**

### **2.1. Population Definitions**

Five subject populations will be considered in the statistical analyses of this study.

- Intention-to-Treat (ITT) population**

The ITT population consists of all subjects randomized into this study.

- Modified Intention-to-Treat (mITT) population**

The mITT population includes all randomized subjects who received at least one dose of study drug and had a baseline lumbar spine BMD measurement and at least one post-baseline lumbar spine BMD measurement.

- Safety population**

The Safety population consists of all randomized subjects who received at least one dose of study drug.

- Per-Protocol (PP) population**

The PP population consists of all mITT subjects who did not have any critical protocol deviations (described in [Section 2.2](#)).

- Antibody Population**

The Antibody population will include subjects in the Safety population who have at least one post-baseline anti-drug antibody assessment.

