Critical protocol deviations are protocol deviations that have the potential to impact the efficacy of the treatment on the subject.

The algorithm to determine critical protocol deviations is in [Appendix B](#) of this SAP. Subjects with at least one critical protocol deviation will be excluded from the PP population. A Per-Protocol Memo with the algorithm in [Appendix B](#) together with the programming specification (“Per Protocol Population Data Set Development”) will be developed and finalized prior to database lock to detail how each of the criteria in the algorithm can be programmed in SAS. The list of subjects with critical protocol deviations identified after applying the algorithm to the SDTM data after database lock will be reviewed and approved internally at Radius in a separate memo. A summary table of reasons for exclusion from the PP population will be presented. A data listing for subjects excluded from the PP population, together with the exclusion reason(s), will be provided.

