### **3. Other date imputations**

Any event with a partial date that requires imputation but has no specific imputation rule will be imputed as follows:

- If the day is missing, then impute the day as '01'
- If the month is missing, then impute the month as 'JUL'
- If the imputation of a start date causes the start date to be post the non-missing end date, then the start date will be imputed as the end date.
- If the imputation of a start date causes the start date to be prior to the start of treatment (but the event should happen post-baseline), then the start date will be imputed as "treatment start date + 1."
- Any date cannot be imputed past the date of death. When this happens, the date will be imputed as the date of death.

**Appendix B. Algorithm to Identify Critical Protocol Deviations that Exclude Subjects from the Per-Protocol (PP) Population**

The below algorithm outlines the criteria for identifying critical protocol deviations. Subjects with at least one of these critical protocol deviations will be excluded from the PP population.

- A. Deviations of subject eligibility (Inclusion/Exclusion criteria) that will result in exclusion from PP population (refer to the protocol for the complete text of each inclusion/exclusion criterion below):
  - 1. Inclusion Criterion #2: Less than 5 years postmenopausal.
  - 2. Inclusion Criterion #3: A BMD T-score outside the required range or fracture criteria not met.
  - 3. Exclusion Criterion #1: History of more than 4 spine fractures, mild or moderate, or any severe fractures.
  - 4. Exclusion Criterion #2: Presence of abnormalities of the lumbar spine that would prohibit assessment of spinal bone mineral density (BMD).
  - 5. Exclusion Criterion #3: Unevaluable hip BMD or subjects who have undergone bilateral hip replacement.
  - 6. Exclusion Criteria #4, #5, #6: Diseases and treatments affecting bone strength.
  - 7. Inclusion Criterion #5: Laboratory tests affecting the bone strength.
  - 8. Exclusion Criteria #16, #17, #18, #19, #20, #21, #22, #23, #24 and #26: Prior treatment with bone-acting agents within the specified time periods.
- B. Deviations of study drug administration that will result in exclusion from PP population:
  - 1. Duration of study drug exposure is less than 3 months (90 days)
  - 2. Compliance to study drug administration < 80%
- C. Deviations of efficacy measurements that will result in exclusion from PP population:
  - 1. Lumbar spine BMD is missing at baseline

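### Exclusion criterion 2 bars lumbar spines that cannot be assessed for BMD, yet its attached definition, at least 2 evaluable vertebrae, describes spines that can be

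*Protocol*

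**What the plan says.** Protocol Section 4.2 excludes any subject who meets a listed criterion. Criterion 2 reads "Presence of abnormalities of the lumbar spine that would prohibit assessment of spinal BMD, defined as having at least 2 radiologically-evaluable vertebrae" within L1–L4, as judged by the central imaging review of the DXA images. The synopsis has the same definition ("defined as having at least 2 radiologically-evaluable vertebrae").

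Two rules beneath the criterion say when a single abnormal vertebra is dropped. One applies when the vertebra is clearly abnormal and cannot be assessed. The other applies when "There is a more than 1.0 T-score difference between the vertebra in question and adjacent vertebrae". Protocol Section 6.6.1 adds only that "Lumbar spine scans must include L1 through L4".

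In the SAP, Appendix B item A.4 lists a breach of the criterion as a reason for exclusion from the PP population. It gives only the opening clause, "Exclusion Criterion #2: Presence of abnormalities of the lumbar spine that would prohibit assessment of spinal bone mineral density (BMD"), with no vertebra count. The introduction to that list tells the reader to "refer to the protocol for the complete text of each inclusion/exclusion criterion below". SAP Section 2.2 says that a Per-Protocol Memo, with its programming specification, "will be developed and finalized prior to database lock to detail how each of the criteria in the algorithm can be programmed in SAS".

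**The concern.** An exclusion criterion should describe the subject who is kept out. The opening clause does so: a spine too abnormal for BMD to be assessed. The definition attached to it describes a spine that can be assessed. A reader who applies the definition gets the opposite result from one who applies the opening clause.

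Lumbar spine BMD is the primary endpoint, and this is the only entry criterion that sets a lumbar vertebra count. Inclusion criterion 3 does not fill the gap, because a subject can qualify on a hip T-score while having few evaluable lumbar vertebrae.

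The wording also reaches the analysis. The primary non-inferiority model is repeated in the PP population (SAP Section 4.4.1.2), and all efficacy endpoints are also analysed there (SAP Section 4.4). A programmer coding item A.4 needs a number and a direction. The SAP gives the direction without a number. The protocol text it refers to gives a number with the direction reversed. Screening and PP coding could therefore treat a subject with few evaluable vertebrae differently.

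**Working it through.** The plan has no figure to reproduce on this point, so the check is one of logic.

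**Inputs.** Let *n* be the number of evaluable vertebrae within L1–L4, so *n* can be 0, 1, 2, 3 or 4. The threshold of 2 is the one printed in criterion 2. Meeting the criterion means exclusion (Protocol Section 4.2).

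**Three readings of the criterion.**

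| *n* | Opening clause with threshold 2 (exclude if *n* < 2) | Printed definition alone (exclude if *n* ≥ 2) | Both clauses required (*n* < 2 and *n* ≥ 2) |
|---|---|---|---|
| 0 | excluded | admitted | admitted |
| 1 | excluded | admitted | admitted |
| 2 | admitted | excluded | admitted |
| 3 | admitted | excluded | admitted |
| 4 | admitted | excluded | admitted |
| Counts excluded | 2 of 5 | 3 of 5 | 0 of 5 |

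The first two readings are complements, so they disagree at 5 of 5 counts. The second excludes a subject whose L1–L4 is fully evaluable. The third excludes nobody and leaves the criterion empty.

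**Does any other text settle the direction together with the count?**

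- The rules beneath criterion 2 say which vertebrae to drop, not how many must remain.
- Protocol Section 6.6.1 says what the scan must cover, not how many vertebrae must be evaluable.
- SAP Appendix B item A.4 has the intended direction but no count, and sends the reader to the protocol for the full text.
- The synopsis repeats the definition, so it cannot correct Section 4.2.
- The Imaging Charter and Imaging Manuals named in Protocol Section 6.6 may give the number, but they are separate documents and were not available for this review.

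No available text states the minimum count in the intended direction.

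**The case against.** The best defence is grammatical. The definition can be attached to the words just before it, the assessment of spinal BMD. The criterion then says that a spine is assessable if it has at least 2 evaluable vertebrae, and that subjects who fall short are excluded. This is probably what was meant. The reverse reading would also be unworkable in a trial whose primary endpoint is lumbar spine BMD, and sites and the central reader have very likely applied the sensible one. That stands, and it limits the practical effect. It does not repair the text: in a list of exclusions, the definition most naturally describes the excluded condition.

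A second defence is that safeguards lie downstream. The judgement belongs to one central imaging review. Appendix B items C.1 and C.2 separately remove subjects with no baseline or no post-baseline lumbar spine BMD. The Per-Protocol Memo is finalised before database lock, and the resulting list of subjects is reviewed internally. These points also stand. They make a coding error less likely, but they do not supply the missing threshold.

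Third, the 5-of-5 disagreement only restates that the two readings are complements. That is correct. It measures the reversal in the wording and says nothing about how many subjects are affected.

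Finally, the SAP was approved in September 2021, and its Section 4.6.5 describes a change of central laboratory midway through the study. Editing the protocol may therefore alter few screening decisions. The documents do not say whether screening had closed. Either way, the PP coding still depends on the criterion.

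**Conclusion.** The concern holds. Criterion 2 is reversed as written, in both the synopsis and Section 4.2. Taken literally, its definition excludes 3 of the 5 possible counts (2, 3 and 4) and admits the 2 (0 and 1) that the opening clause is meant to exclude.

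The consequence is limited. The mITT population is primary for efficacy, and its definition ("The mITT population includes all randomized subjects who received at least one dose of study drug", with baseline and post-baseline lumbar spine BMD) carries no eligibility condition. The sample size and power calculation are untouched, and no loss of the PP population is shown. The number of subjects concerned cannot be derived from the documents.

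The conclusion assumes that the intended threshold is the printed 2 and that the Imaging Charter does not set a different one. The correction should be made, but it does not threaten the primary analysis.

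**What to change.** In the synopsis and in Protocol Section 4.2, change the definition in criterion 2 to *fewer than 2 radiologically-evaluable vertebrae within L1–L4*, keeping the reference to central imaging review. This retains the sponsor's threshold and corrects only the direction. Check it against the Imaging Charter.

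State the same threshold in SAP Appendix B item A.4, and program the Per-Protocol Memo from the corrected text before database lock.

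The cost is one phrase in two protocol places, one clause in the SAP and a check of the Memo. Intended enrolment does not change if the printed threshold is the intended one. If screening is already complete, the SAP and Memo changes are the ones that still matter.
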